Study objectives and endpoints	
Objectives are set in the context of high-risk patients diagnosed with localised prostate cancer scheduled for robot-assisted RP who have not had neoadjuvant ADT, and are listed below.
 
Primary objectives:
 
To establish the value of CTC positivity in predicting post-RP treatment failure, including BCR and new lesions detected by cancer imaging.
 
To establish the value of a combined CTC test (including CTC enumeration and gene expression) in predicting post-RP treatment failure and the time of the development of BCR and new lesions detected by cancer imaging.
 
Secondary objectives
 
To investigate the potential of CTCs in predicting positive lymph node metastasis, which affects the selection and scale of RP as the initial treatment.
 
To assess potential for convenient non-invasive disease monitoring

Protocol for spin off research project- Circulating tumour cells as biomarkers to predict prostate cancer metastasis for treatment stratification of localised cancer

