	
To provide a preliminary assessment of the prognostic value of CTC data (positivity and gene expression) in predicting post-RP PCa metastasis development, overall survival and cancer specific survival.
 
To provide evidence and data which can be used to design a future clinical trial of a CTC- based intervention to be used to guide therapeutic choice in the management of high-risk localised PCa.
 
To evaluate the longer-term prognostic value of CTC detection and CTC gene expression for metastases and cancer-specific survival.
 
Primary endpoint
 
The primary outcome is post-RP treatment failure during the first 4.5 years of follow up from start of recruitment.
 
Post-RP treatment failure is defined as a PSA $\geq 0.2\text{mg/ml}$ at the routine PSA test 3 months after RP (commonly called 'failure to nadir') and remaining at this level or further increase afterwards without further treatment, or imaging detected appearance of cancer lesions.
 
Cancer lesions detected by imaging without a PSA rise might include neuroendocrine PCa and lesions detected by PSAM-PET. This combined post-RP treatment failure primary endpoint will maximally capture all the clinically significant cancer appearance events.
 
Secondary endpoints
 
BCR during the first 4.5 years of follow up: PSA $\geq 0.2\text{ng/ml}$ at any time post-RP and remaining at this level or further increase afterwards without further treatment.
 
Metastasis (any location)-free survival during the first 4.5 years of follow up. Only 5% of subjects with distant metastasis event (based on traditional imaging technologies) within this time frame (4-6).
 
Metastasis (any location)-free survival at 10 years follow up. to confirm that metastatic event rates have increased among the positives, i.e. a declining rate of "false positives".
 
Deaths from any cause during the first 4.5 years of follow up
 
Overall survival at 10 years of follow up.
 
Prostate cancer specific deaths during the first 4.5 years of follow up. Expected to be 2% or less based on previous studies in the post RP context.
 
Prostate cancer specific survival at 10 years of follow up. Our hypothesis is that most if not all of the patients dying of PCa will be in the CTC positive group.

Target sample size	294

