Accuracy of the CTC scores alone and in combination with CTC gene panel expression data in determining RP treatment failure, i.e. BCR and/or metastasis via imaging, in particular PSMA-PET, over the study period will be measured. The prognostic value of CTC data will also be investigated for BCR, PSMA-PET detected cancer lesions, metastasis event, overall survival and cancer specific survival outcomes (see below statistical analysis plan section). At the end of this project, we expect to generate robust data to determine whether CTCs detectable in patients with high-risk localised PCa at pre- and post-RP can predict RP treatment failure and a CTC gene panel will further enhance the prediction value of CTCs for post-RP cancer progression.

Statistical methodology and analysis

The primary analysis is the estimation of the sensitivity of the pre-surgery CTCs for detection of RP treatment failure, i.e. BCR or progression detected by imaging. Observed specificity, positive and negative prediction values will be reported. Prevalence of events and specificity will be presented over time. BCR-free survival will be estimated and Kaplan-Meier curves presented. Preliminary investigation of the prognostic value of pre-surgery CTC data in terms of predicting survival outcomes will be investigated. CTC data will be explored alongside other pre-surgery risk factors using multivariate analysis. Recurrence events and follow up CTC results will be reported and compared over time.

Statistical considerations

1). Definitions:

- **CTC score and result:** CTCs will be identified based on the immunofluorescence staining as CK⁺/VIM⁻/CD45⁻, CK⁺/VIM⁺/CD45⁻, and CK⁻/VIM⁺/CD45⁻ CTCs as described above in lab procedure Part IV. Positive CTC score were defined based on our previous data as any CK⁺/VIM⁺/CD45⁻, CK⁺/VIM⁺/CD45⁻ and/or >3 CK⁻/VIM⁺/CD45⁻ cells identified in the PCa patients.
- **CTC gene-expression result:** a binary (negative/positive) result based on the gene-expression profile from within the blood sample indicating the amount of genes expressed in CTCs from the PCa patients.

Protocol for spin off research project- Circulating tumour cells as biomarkers to predict prostate cancer metastasis for treatment stratification of localised cancer

- **Combined CTC result:** a binary (negative/positive) result based on both CTC number and gene-expression profile where a positive result indicates a patient should be considered to have high metastatic potential.

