- **MRI score:** Multi-parametric MRI Likert scale 1-5 where >3 indicates aggressive cancer.
- **BCR:** PSA $\geq 0.2\text{ng/ml}$ at any time post-RP and remaining at this level or further increase afterwards without further treatment (see Table 4 for endpoint definitions)
- **Post-RP treatment failure:** (see Table 4 for endpoint definitions)

2). Sample size

The study hypothesis is that the presence of CTCs has close to 100% sensitivity and specificity for micro-metastasis, and thus RP treatment failure. Due to the long-term nature of recurrence events, there will be a proof of principle part to this study which occurs within the funded study timeframe of 5 years, and an intention to collect and analyse relevant longer-term events at 10 years (see section 4 for objectives and endpoints). The primary endpoint is **post-RP treatment failure**, the majority of which will be due to BCR. Despite the long-term nature of events of interest, it will be possible to provide a timely estimate of sensitivity, since of those who do have an observable BCR event, most if not all are expected to have a positive CTC result. Thus, consistent with previous work, this study estimates predicting post-RP cancer events with 95% sensitivity. During the first 4.5 years of follow up, the hypothesised prevalence of BCR events to be at least 40%.

In order to confirm an expected sensitivity of 95% within 5% precision either side of a 95% confidence interval (CI) in a sample with an underlying prevalence of 40%, requires at least 73 events, that is at least 183 recruited individuals. Inflate this by 8.5% to a target recruitment of 200 to ensure suitability of samples and measurable outcomes.

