The recruitment plan will be 200 patients in the first two years of the 5-year project to allow an approximate 3.5 to 4 year median follow up. Specificity is important considering the future circumstance of potentially denying patients curative surgery, if a CTC test indicates metastasis. A study size of 200 and 120 true negatives would give a 97.5% lower confidence limit on a specificity of 99% (1% false positive rate). However, it is anticipated the specificity will be low due to positive results for those who recur beyond the 5-year study. Assuming these events are due to micro-metastases at the time of surgery, observed sensitivity and specificity will be used, plus additional analyses assuming up to 20% of the events occur after the funded 5-year project⁴⁻¹¹ to estimate the real false positive and negative rates.

3). Method of analysis

Study flow and patient characteristics will be reported. Measures of accuracy will be presented with 95% confidence intervals (CIs). The primary analysis is the estimation of the sensitivity of the pre-surgery existence of CTCs for detection of RP treatment failure, i.e. BCR or progression detected by any imaging at the 4.5-year follow-up time point. Observed specificity, positive and negative prediction values will also be reported at 4.5 years of follow up, with a note to indicate that these estimates are subject to change given the long-term nature of recurrence events. Specificity will be presented over time and additional analysis accounting for artificial inflation of false positives based on increasing prevalence of events. BCR-free survival will be estimated and Kaplan-Meier curves presented.

The number of participants with recorded metastases, lymph node metastases, deaths from any cause and PCa deaths during the first 4.5 years of follow up

Protocol for spin off research project- Circulating tumour cells as biomarkers to predict prostate cancer metastasis for treatment stratification of localised cancer

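### The primary analysis and the sample size rest on sensitivity alone, which cannot by itself show that CTC positivity predicts treatment failure

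*Protocol*

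**What the plan says.** Protocol section 3 (Table 1, statistical methodology) and section 7 (Statistical methodology and analysis) both give the primary analysis in the words "The primary analysis is the estimation of the sensitivity of the pre-surgery CTCs for detection of RP treatment failure". Section 7, Method of analysis, repeats it for the 4.5-year time point: "The primary analysis is the estimation of the sensitivity of the pre-surgery existence of CTCs for detection of RP treatment failure".

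The first primary objective (Table 1; also Aim I in section 2.2) is broader: "To establish the value of CTC positivity in predicting post-RP treatment failure, including BCR and new lesions detected by cancer imaging". The hypothesis at the start of section 7, Sample size, covers both measures, with sensitivity and specificity each close to 100%.

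The number of men follows from sensitivity only. The same section works from an expected 95% sensitivity with 5 points of precision and an "underlying prevalence of 40%, requires at least 73 events, that is at least 183 recruited individuals", inflated to 200. It justifies an early answer because "it will be possible to provide a timely estimate of sensitivity, since of those who do have an observable BCR event", most or all should be CTC positive.

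On specificity, the same section says that it matters, because a positive test might in future lead to surgery being withheld, and gives a precision figure for a specificity of 99%. It then adds: "However, it is anticipated the specificity will be low due to positive results for those who recur beyond the 5-year study". Further analyses assume that up to 20% of events fall after the funded period. Specificity, PPV and NPV are reported at 4.5 years with 95% CIs and a note that they may change. Cox regression on survival outcomes is called preliminary, and multivariate work is exploratory.

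**The concern.** Sensitivity is the share of CTC positives among men who fail. It contains no information on men who do not fail, so it cannot show whether positivity differs between the two groups, and that difference is what predictive value means. The quantity that the study is built to estimate precisely therefore does not answer the primary objective by itself.

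The measures that would complete the answer sit outside the primary analysis. One of them, specificity, is expected in advance to be low, with no figure for how low would still fit the hypothesis. At stake is how the 4.5-year result will be read. Aim IV uses these data to design a trial of CTC-guided treatment choice, and the protocol itself says why false positives would matter there.

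**Working it through.** **1. The plan's own figures (section 7, Sample size).** Inputs: sensitivity 0.95, half-width 0.05, two-sided 95% CI, prevalence 0.40, inflation 8.5%.
- Events: 1.96² × 0.95 × 0.05 / 0.05² = 72.99, so 73.
- Men: 73 / 0.40 = 182.5, so 183.
- Inflated: 183 / (1 − 0.085) = 200.

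All three reproduce. The specificity sentence reproduces as a one-sided 95% limit: 0.99 − 1.645 × √(0.99 × 0.01 / 120) = 0.975. It describes what 120 men would give and does not drive the sample size.

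**2. An uninformative test.** If CTC status is independent of outcome, P(CTC+ | failure) = P(CTC+). The protocol gives no overall positivity rate, so 95% is an assumption. With 200 men and 40% failing (80 failures, 120 non-failures):

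| | Failure | No failure |
|---|---|---|
| CTC+ | 76 | 114 |
| CTC− | 4 | 6 |

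- Sensitivity 76/80 = 95% (Wald 95% CI 90.2 to 99.8; exact 87.7 to 98.6).
- Specificity 6/120 = 5% (exact 1.9 to 10.6).
- PPV 76/190 = 40%, the prevalence. NPV 6/10 = 60%, one minus the prevalence.
- Sensitivity + specificity − 1 = 0.

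**3. Range over the assumed positivity rate.** Binomial probability that an uninformative test shows an observed sensitivity of at least 90%:

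| Positivity in all men | 73 failures | 80 failures |
|---|---|---|
| 95% | 0.97 | 0.98 |
| 90% | 0.55 | 0.59 |
| 85% | 0.13 | 0.13 |

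**4. How much low specificity late failures can explain.** Take a perfect test, so that every late failure counts as a false positive at 4.5 years. The 20% allowance can be read in three ways:
- The 80 early failures are 80% of all failures, so 20 are late: (120 − 20)/120 = 83%.
- Late failures are 20% of 80, so 16: (120 − 16)/120 = 87%.
- 20 percentage points of 200 men, so 40: (120 − 40)/120 = 67%.

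For the uninformative test in step 2, assigning every late failure to the CTC-positive group raises specificity only to 6/104 = 5.8%, 6/100 = 6% or 6/80 = 7.5%.

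**5. Can the planned sample compare the two groups?** With 80 failures and 120 non-failures:
- Sensitivity 95%, false-positive fraction 80%: difference 0.15, SE = √(0.0475/80 + 0.16/120) = 0.0439, 95% CI about 6 to 24 points. Power to separate 95% from 80% positivity is about 88% (two-sided 5%).
- Both 95%: difference 0, SE = √(0.0475/80 + 0.0475/120) = 0.0315, 95% CI about −6 to +6 points.

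**6. Late failures and the direction of this difference.** If late failures are CTC positive at least as often as men who never fail, the false-positive fraction at 4.5 years is no lower than that of men who never fail. A positive difference then keeps its sign when all failures are counted. Without that condition it need not. Take 80 early failures 80% positive (64), 20 late failures 40% positive (8) and 100 men who never fail 80% positive (80). At 4.5 years: 64/80 − 88/120 = 80.0% − 73.3% = +6.7 points. With all failures: 72/100 − 80/100 = −8 points.

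**The case against.** A reader might infer that the protocol would declare success on a worthless test, or that poor specificity could never count against it. The documents do not support either reading.
- The 95% ± 5 points is a precision goal for sizing. No success rule is attached to it, and the statistical analysis plan, which is not shown, could hold a rule for claims.
- Specificity, PPV and NPV are reported with intervals at 4.5 years, and CTC results are presented for the whole cohort with analysable samples. In the example above, 5% specificity and a PPV equal to the prevalence would plainly contradict the stated hypothesis.
- The allowance for late events is bounded at 20% of events, the 5-year part is called proof of principle, and a 10-year check is planned on whether the rate of false positives declines.
- The 95% positivity rate is illustrative, and the effect fades quickly below 90%.

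All of this stands. It limits the point to what the primary analysis can show and does not remove it. The informative measures are planned, but none is primary, and no passage links specificity to the conclusion about predictive value or says what level the late-event allowance can justify. The Kaplan-Meier curves are not said to be split by CTC status.

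**Conclusion.** The point holds in a limited form. The primary analysis and the sample size rest on a measure that cannot by itself answer the primary objective. This follows from the definition of sensitivity and needs no assumption. How easily an uninformative test could resemble the planned result depends on the unknown overall positivity rate: very likely at 95%, about even at 90%, unlikely at 85%. The plan's own 20% allowance explains specificity down to about 83–87% (67% on the widest reading), assuming a perfect test and 40% early failures. Values well below that would be evidence against the test, and the protocol should say so.

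The same logic applies to the secondary hypothesis on deaths, "Our hypothesis is that most if not all of the patients dying of PCa will be in the CTC positive group", which any test positive in most men would satisfy. That is minor, because CTC results among the deaths and for the whole cohort are already to be reported.

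This is a worthwhile improvement to the design. The planned analyses are not invalid.

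**What to change.** - Make sensitivity and the false-positive fraction at 4.5 years, in the same men, the joint primary result. Report their difference (sensitivity + specificity − 1) with its 95% CI.
- State that predictive value will be claimed only if the lower limit of that difference is above 0.
- State that meeting this condition shows association only. A test with 95% sensitivity and 20% specificity would be expected to pass, so it says nothing about clinical usefulness.
- State that the condition is conservative for late failures only if they are CTC positive at least as often as men who never fail. This is the protocol's own assumption and should be written down as such.
- Replace the open expectation of low specificity with the level that the 20% allowance can explain, say which reading of the 20% is meant, and treat values well below that level as evidence against the test.

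The cost is protocol wording and one interval from counts already tabulated, with no more patients or data. The downside is a stricter condition for claiming predictive value.

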Each patient will be allocated a unique ID and will be used by the lab research team. This unique ID will be recorded in the tissue bank database for future correlation analysis of the CTC results with clinical follow-up data. Sample processing will be performed in tissue culture hood in the designated lab. The whole blood sample will be processed within 4hrs for CTC analysis after collection. Standard Operating Procedure (SOP) (C-ProMeta-1) that is generated describing sample process and analyses need to be followed. There will be fewer patients for the post-RP than the pre-surgery blood collection based on patient exclusion criteria after RP.

Based on the sample size calculation 200 patients will be recruited for both pre- and post-surgery blood sample collections for CTC analysis, which are expected to be achieved within the first two years of the project.

Patient informed consent (including the permission to conduct remote longer-term follow-up) and blood sample collection will be performed by the CRF or the clinical care team.

All patients will have a PSA test at 3 months after their RP during a routine follow-up at UCLH. A PSA ≥ 0.2 will be recorded as a treatment failure event and PSMA-PET scans will be performed as standard clinical care at the study hospitals to detect small PCa lesions. After 3 months, patients are referred back to their original referring centres. Patients with negative PSA results at three months will be followed up by telephone or online app by the study CRF in order to ascertain whether subsequent PSA tests are positive (PSA ≥ 0.2), indicating BCR, metastasis occurs as detected by cancer imaging including PSMA-PET scan or if they have received salvage treatment with hormones/radiotherapy. In addition, details of long term follow up, such as post-operative PSA results and record of adjuvant therapies, will be sourced from patients' hospital electronic medical records, or requested from their local GP or health centre. All patients will be followed-up until the end of the project for metastasis progression as detected by imaging, PCa-specific death and death from any causes. In addition to data collected within the 5-year funded period, we plan to conduct remote longer-term follow up with fully informed consent from patients at point of enrolment, including:

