will be reported alongside the number of these participants with a positive by CTC result, and positive combined CTC result. Metastases-free, PCa-specific and overall survival will be reported during the 5 years study time frame and it is intended to perform a later analysis at 10 years of follow up. Preliminary investigation of the prognostic value of pre-surgery CTC data in terms of predicting survival outcomes will be investigated using Cox regression, with hazard ratios reported with associated 95% CIs. CTC data will be explored alongside other pre-surgery risk factors such as plasma PSA using multivariate analysis. Recurrence events and follow up CTC results will be reported and compared over time. The above analyses will be applied to the CTC gene panel. The gene panel will also be correlated with the pre- and post- RP CTC number changes and cancer progression events.

CTC results will be presented for the whole cohort who provided analysable blood samples and stratified by those included in the above analyses, and those excluded due to reasons such as a positive surgery margin, other evidence of locally remaining disease, and who subsequently have adjuvant ADT or radiotherapy.

8. Ethics

The study is a spin out project of the parent project authorised under RLTB ethics, where the main research tissue bank approval provided by the London City & East Research Ethics Committee.

9. Data handling, storage and record keeping- to describe who and how the data will be handled, which data nodes will be used, where it will be stored and security of the data

The CRF (funded by QMUL, but with contract at UCLH) will be part of the study management group and will act as the contact point between UCLH and QMUL. Under the MTA and data sharing agreement (DSA) between the two institutions and with patient consent, the CRF will collect blood samples during pre-surgery operation and after the surgery during the first PSA follow-up visit at UCLH.

The following clinical data will be collected for each patient by the CRF:

- Histology reports
- Clinical stage
- Prostate Specific Antigen (PAS) (pre- and post-surgery)
- Imaging (MRI, PSMA-PET/CT and bone scan)
- Results and record of adjuvant therapies
- Treatment date and method for post-surgery cancer recurrence

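### The only printed rule for a positive CTC score lists CK+/VIM+ twice and omits CK+/VIM−; confirm and correct it before CTC results are linked to outcomes

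*Protocol*

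**What the plan says.** The rule is in section 7 of the protocol, Statistical considerations, part 1 (Definitions), under CTC score and result. The first sentence names the cells that count as CTCs: "CTCs will be identified based on the immunofluorescence staining as CK⁺/VIM⁻/CD45⁻, CK⁺/VIM⁺/CD45⁻, and CK⁻/VIM⁺/CD45⁻ CTCs". For detail it points elsewhere, "as described above in lab procedure Part IV". The next sentence defines a positive score "as any CK⁺/VIM⁺/CD45⁻, CK⁺/VIM⁺/CD45⁻ and/or >3 CK⁻/VIM⁺/CD45⁻ cells identified in the PCa patients", and attributes this to the group's earlier data. No other part of the supplied protocol prints a positivity rule. Section 6 refers laboratory work to a separate document: "Standard Operating Procedure (SOP) (C-ProMeta-1) that is generated describing sample process and analyses need to be followed".

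The first primary objective in Table 1 depends on the result of this rule: "To establish the value of CTC positivity in predicting post-RP treatment failure, including BCR and new lesions detected by cancer imaging". Section 7, part 3 (Method of analysis) makes sensitivity of the pre-surgery CTC result for treatment failure the primary analysis. It also says that the numbers with metastases, deaths from any cause and prostate cancer deaths "will be reported alongside the number of these participants with a positive by CTC result".

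**The concern.** Two adjacent sentences do not agree. The first has three entries, all different. The second also has three entries, but two are identical, and the phenotype left out is one that the first sentence calls a CTC. A duplicated entry adds nothing to a list joined by and/or, so the printed rule is unlikely to be what was meant.

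At stake is the definition of the index test. A reader with the protocol alone could not reproduce the intended test with certainty. Timing matters too. Treatment failure can be recorded from three months after surgery, CTC analysis runs to year 3, and the statistical analysis starts after 4.5 years. If the ambiguity is settled only after results and outcomes have been joined, the choice could look as if it was made to suit the findings.

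**Working it through.** **Step 1. The planned figures.** The inputs are in section 7, part 2 (Sample size): expected sensitivity 95%, precision ±5 points, 95% confidence, prevalence 40%.

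- Events: 1.96² × 0.95 × 0.05 / 0.05² = 72.99, rounded up to 73.
- Men: 73 / 0.40 = 182.5, rounded up to 183.
- Inflation: 183 / (1 − 0.085) = 200.0 (183 × 1.085 = 198.6, which is also close to 200).

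This agrees with the protocol, which "requires at least 73 events, that is at least 183 recruited individuals", and with its target of 200. No phenotype count enters the calculation, so correcting the rule leaves 73, 183 and 200 unchanged.

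**Step 2. The two sentences side by side (all CD45−).**

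| Phenotype | Identified as a CTC | In the positivity rule |
|---|---|---|
| CK+/VIM− | yes | absent |
| CK+/VIM+ | yes | any, listed twice |
| CK−/VIM+ | yes | more than 3 |

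**Step 3. Where the rules differ.** Let a, b and c be a man's counts of CK+/VIM−, CK+/VIM+ and CK−/VIM+ cells.

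- Printed rule: positive if b > 0 or c > 3.
- Probable rule (an assumption): positive if a > 0 or b > 0 or c > 3.

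Over a = 0 to 5, b = 0 to 5 and c = 0 to 7 there are 6 × 6 × 8 = 288 patterns. The rules disagree only when a ≥ 1, b = 0 and c is 0, 1, 2 or 3, which is 5 × 1 × 4 = 20 patterns. In all 20 the printed rule gives negative and the probable rule positive.

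**Step 4. Direction.** Every man positive under the printed rule is also positive under the probable rule. So the printed rule cannot give higher sensitivity or lower specificity. Positive and negative predictive values can move either way, because numerator and denominator both change. If CK+/VIM− cells were meant to count only above some cut-off, fewer patterns would differ, but the direction would be the same.

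**Step 5. Scale per man.** With 200 men and 40% prevalence there are 200 × 0.40 = 80 failures and 200 × 0.60 = 120 men without failure, in line with the protocol's "A study size of 200 and 120 true negatives". Each man with the affected pattern moves:

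- sensitivity by 1/73 = 1.37 points at the minimum 73 events, or 1/80 = 1.25 points at 80, if he fails;
- specificity by 1/120 = 0.83 points, if he does not.

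Four such men among 80 failures would move sensitivity by 4/80 = 5 points, which is the whole planned precision margin.

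**Step 6. Illustration, on assumed shares.** Suppose the probable rule has 95% sensitivity, and a share s of the failing men who test positive are positive only through CK+/VIM− cells. The printed rule then has sensitivity 0.95 × (1 − s): 93.1% at s = 2%, 90.3% at 5%, 85.5% at 10% and 76.0% at 20%. The protocol gives no basis for choosing among these shares, and zero is possible.

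**The case against.** The finding rests on one superscript sign in text read from a PDF by a program, so a misreading is possible. This stands as a possibility, but it is not the likelier explanation: the four minus signs in the rule, and the five in the sentence before it (including VIM−), read as expected. Checking the source PDF settles the matter.

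The rule the laboratory actually uses may be in SOP C-ProMeta-1 or the cited lab procedure, neither of which is in the supplied text. This also stands, and it is why nothing here says that the laboratory scores samples wrongly. But a correct SOP would not cure the protocol: the two would then disagree on the primary test.

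The Method of analysis speaks of the existence of CTCs before surgery. Read literally, that would make any recognised CTC a positive result, so the score rule would not touch the primary sensitivity. The wording does leave room for this. However, the primary objective refers to CTC positivity, and existence alone would also override the requirement of more than three CK−/VIM+ cells. Even on this reading, the statement that sensitivity falls or stays the same remains true.

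Finally, the documents do not prove that a single CK+/VIM− cell should be enough. This is correct, and the replacement wording is therefore only the probable one, to be confirmed from the sources.

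**Conclusion.** The concern holds. As printed, the only positivity rule in the protocol contradicts the sentence before it by repeating CK+/VIM+ and leaving out CK+/VIM−. It should be fixed, because it defines the test in the first primary objective.

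The effect on results is unknown and may be zero: the protocol gives no phenotype frequencies, and the laboratory may already work to a correct rule. Only the direction is firm. If followed literally, the printed rule cannot raise sensitivity and cannot lower specificity relative to the probable rule. This rests on two assumptions: that the supplied text reproduces the PDF faithfully, and that CK+/VIM− cells were meant to count towards a positive score. Confidence is medium for that reason.

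**What to change.** Before CTC results are linked to outcomes:

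1. Check the sentence against the source PDF, SOP C-ProMeta-1 and the earlier data from which the rule was derived.
2. Correct the duplicated entry. The intended rule is probably: any CK+/VIM−/CD45− cell, any CK+/VIM+/CD45− cell, and/or more than three CK−/VIM+/CD45− cells. Confirm from those sources whether CK+/VIM− counts from one cell or above a cut-off.
3. If the cited lab procedure Part IV is not part of the protocol, cite the SOP there instead.

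The cost is one line of protocol wording. Design, sample size, blood samples and laboratory work do not change.

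### The printed precision for sensitivity (within 5 points from 73 events) and specificity (97.5% lower limit from 120 non-events) rests on a normal approximation that is too optimistic at these counts

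*Protocol*

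**What the plan says.** All of this is in Protocol section 7, under Statistical considerations.

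- **Sensitivity (item 2, Sample size).** The aim is set out as "In order to confirm an expected sensitivity of 95% within 5% precision either side of a 95% confidence interval". At a prevalence of 40% this "requires at least 73 events, that is at least 183 recruited individuals". The next step is "Inflate this by 8.5% to a target recruitment of 200".
- **Specificity (item 2, Sample size).** A study of 200 with "120 true negatives would give a 97.5% lower confidence limit on a specificity of 99" per cent. Whether the limit is one-sided or two-sided is not stated. The text then concedes that "it is anticipated the specificity will be low due to positive results for those who recur beyond the 5-year study".
- **Analysis (item 3, Method of analysis).** The primary analysis is the estimation of sensitivity. Accuracy measures are to be reported with 95% confidence intervals; the interval method is not named.

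**The concern.** The plan assumes proportions close to 100% with few misclassified patients: 73 × 0.05 = 3.65 false negatives and 120 × 0.01 = 1.2 false positives. A symmetric normal-theory interval works badly there. It can run to or past 100%, and it puts the lower limit too high.

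A reader of the section will take away a lower limit of 90% for sensitivity (95 minus 5) and 97.5% for specificity. The first is the stated justification for 73 events, 183 patients and the target of 200. The second bears on the protocol's own worry about denying curative surgery to patients wrongly classed as having micro-metastases. If the study reports its results with a sound interval, the limits will be visibly worse than promised even when the test performs exactly as hypothesised.

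**Working it through.** **Inputs, all from section 7, Sample size:** sensitivity 95%, precision ±5 points, 95% interval, prevalence 40%, inflation 8.5%; specificity 99%, 120 patients without an event.

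**1. Reproducing the protocol's figures (Wald).**
- Events: 1.96² × 0.95 × 0.05 / 0.05² = 72.99, rounded up to 73.
- Patients: 73 / 0.40 = 182.5, rounded up to 183; 183 / (1 − 0.085) = 200.
- Specificity limit: 0.99 − 1.645 × √(0.99 × 0.01 / 120) = 0.99 − 1.645 × 0.00908 = 0.9751 (one-sided 95%). The two-sided version is 0.9722 at exactly 99%, or 0.9754 at 119/120.

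So the printed numbers are not calculation slips. The implied sensitivity interval is 90.0% to 100.0%. The two-sided Wald interval at 99% specificity is 97.2% to 100.8%, which passes 100%.

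**2. Is the approximation adequate here?** Summing binomial probabilities over all outcomes gives the true coverage of a nominal 95% interval:

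| Setting | Wald | Wilson | Exact |
|---|---|---|---|
| n = 73, p = 0.95 | 88% | 95% | 97% |
| n = 120, p = 0.99 | 70% | 97% | 99% |

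**3. Sensitivity.** Wilson limits are [p + z²/2n ± z√(p(1−p)/n + z²/4n²)] / (1 + z²/n). With p = 0.95, n = 73, z = 1.96: (0.9763 ± 0.0565) / 1.0526 = 0.8738 and 0.9812. Exact limits are Clopper-Pearson. The first row uses the fractional count 0.95 × 73 = 69.35.

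| Detected / events | Wilson 95% | Half-width | Exact 95% | Half-width |
|---|---|---|---|---|
| 69.35/73 (95%) | 87.4–98.1% | 5.4 | 87.2–98.7% | 5.8 |
| 69/73 | 86.7–97.8% | 5.6 | 86.6–98.5% | 6.0 |
| 70/73 | 88.6–98.6% | 5.0 | 88.5–99.1% | 5.3 |
| 76/80 (95%) | 87.8–98.0% | 5.1 | 87.7–98.6% | 5.5 |

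At 95% with 73 events the lower arm is 7.6 points (Wilson) or 7.8 (exact). The 76/80 row is the best case at the full target: all 200 evaluable and 40% with events. A lower limit of 90% with 73 events requires at least 71 detected; if the true sensitivity is 95%, the probability of that is 29%.

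**4. Specificity.** For 119/120 the two-sided Wilson lower limit is (1.0077 − 0.0228) / 1.0320 = 0.9543.

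| Lower limit | Wilson | Exact |
|---|---|---|
| 119/120, two-sided 95% | 95.4% | 95.4% |
| Exactly 99% of 120, two-sided 95% | 95.2% | 95.2% |
| 119/120, one-sided 95% | 96.4% | 96.1% |
| Exactly 99% of 120, one-sided 95% | 96.1% | 95.8% |
| 120/120, two-sided 95% | 96.9% | 97.0% |

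Even with no false positives at all, the two-sided limit stays below 97.5%. An exact one-sided 95% limit reaches 97.5% only at 120/120, which is 100% specificity and not the stated 99%.

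**5. Scale of the gap.** At 95% sensitivity, a half-width of 5 points needs 83 events (Wilson) or 94 (exact); a lower limit of 90% needs 139 or 142. At 99% specificity, a lower limit of 97.5% needs 416 to 417 non-events two-sided, or 294 to 318 one-sided, against 120. These counts show the size of the discrepancy; they are not a request for more patients.

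**The case against.** The strongest reply is that nothing is miscalculated. The protocol used the standard precision formula for a single proportion, and that formula returns 73, 183 and 200. Read as a half-width, the shortfall is small: 5.4 to 5.8 points at 73 events, 5.1 to 5.5 at 80, and 70/73 gives a Wilson half-width of just under 5. The protocol never prints a 90% lower limit, and it presents 40% prevalence and 73 events as minimum values. The choice of interval is normally settled in the statistical analysis plan, which is not at hand, and nothing says Wald limits will be reported. On specificity, the sidedness is unstated, so part of the gap between 97.5% and 95% may be sidedness rather than method. The figure sizes nothing, and the next sentence already expects specificity to be low.

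Much of this stands, and it limits the weight of the point. It does not rescue the printed figures. The text promises 5 points on each side, and at an observed 95% neither 73 nor 80 events delivers that by Wilson or exact limits. On a one-sided reading the specificity limit at 119/120 is still 1.1 to 1.4 points short. The criticism is of two numbers the protocol prints, not of a method left to another document: an analysis plan that used Wilson or exact limits would contradict those numbers, and one that used Wald would carry the poor coverage into the primary result.

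**Conclusion.** The point holds, with modest weight. Under the protocol's own assumptions, the two-sided 95% lower limit for sensitivity is about 87% to 88%, not 90%. For specificity it is about 95%, or about 96% one-sided, not 97.5%. The overstatement is 2 to 3 points for sensitivity and about 2 points for specificity (1.1 to 1.4 if one-sided).

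This rests on three assumptions: that the printed figures come from a Wald formula, which is inferred because it returns both; that the 95% interval for sensitivity is two-sided; and that the 120 true negatives are the 120 patients without an event. No threshold, stopping rule or go/no-go decision depends on these limits, so the design is unaffected. What is wrong is the stated precision, including that of the primary analysis.

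**What to change.** Keep the target of 200 and restate the precision in section 7, Sample size, naming the interval method and sidedness with each figure:

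1. *Sensitivity:* with 73 events and 95% sensitivity, the two-sided 95% interval is about 87% to 98% (Wilson; exact 87% to 99%).
2. *Specificity:* replace the 97.5% figure with a statement that, with 120 non-events, an observed specificity of about 99% has a two-sided 95% lower limit of about 95% (Wilson or exact).

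The cost is two sentences of protocol text, with no extra patients, data or analyses. The only drawback is that the advertised precision looks slightly less favourable.
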